5.3.1 Labeling

Primary packaging: Label for vial: single panel (rh-NGF or Vehicle):

Label for vial: single panel

Line No.	Text	Comments
1	NGF0117	
2	Dompé farmaceutici s.p.a	
3	rhNGF 20 µg /ml or Vehicle	
4	Administration eye: RIGHT or LEFT	Active/placebo or placebo/placebo according to the randomization list stratified per eye and per subject
5	Eye drops (1 ml)	
6	Batch: <vvvv>	Codified batch
7	Kit XXXX	Format of kit no.: "XXXX"
8	CAUTION: New Drug-Limited by Federal (or United States) law to investigational use	

* The number of KIT is reported according to the randomization list that will be generated and balanced by gender, study eye and treatment

Secondary packaging: Six day kit (containing 6 vials): tear-off panel

Line No.	Text	Comments	Tear Off part of the label
1	Protocol no.: NGF0117		To be enclosed
2	Sponsor: Dompé farmaceutici s.p.a, [name]		To be enclosed
3	rhNGF 20 µg/ml or Vehicle		To be enclosed
4	Eye drops solution (1 ml per vial)		
5	Contains: 6 multidose vials		
6	Directions for use: refer to dosing instructions		
4	Administration eye: RIGHT or LEFT	Active/Placebo or Placebo/Placebo according to the randomization list stratified per eye and per subject	To be enclosed
7	Batch: <vvvv>\	Codified batch	To be enclosed
8	Kit XXXX	Format of kit no.: "XXXX"	To be enclosed
9	Subj. Screening #: S□□□		To be enclosed
10	Subj. Randomization #: □□□□		To be enclosed
11	Store in a freezer at -20°C at the Investigational site		
12	Store in a refrigerator at 2-8 °C (36°F to 46°F) during 6 days treatment period		
13	Do not shake		
14	Keep out of the reach of children		
15	For clinical trial use only		
16	CAUTION: New Drug-Limited by Federal (or United States) law to investigational use		

5.3.2 Supply, Storage and Handling of IMP

rhNGF must be stored at -20°C in an appropriate locked room accessible only to the pharmacist, the Investigator, or a duly designated person.

Daily vials containing rhNGF are thawed at 2 to 8°C in the carton and protected from light. Because rhNGF does not contain preservatives, the contents of each vial are for daily-use only and opened vials must be maintained at 2 to 8°C and used within 12 hours. Agitation of vials may cause foaming and/or particle formation.

Protect vials from light. Do not shake vials.

Administration

Drug preparation and administration instructions will be provided separately in the Pharmacy Manual for the study.

5.3.3 Replacement Kits

Thirty additional kits will be prepared as replacements. Assignment of subject and kit number is described in § 6.1).

5.4 Dose, Route And Schedule Of Imp Administration

5.4.1 Administration route

The Administration route is ophthalmic, to be applied by investigator at site.

5.4.2 Dose regimen

In all subjects both eyes will be treated; with one eye as the study eye.

- All subjects will receive either rhNGF or vehicle in the study eye (right or left) according to the randomization list.
- The fellow (non-study) eye will receive vehicle.

Both the subjects and the investigator/ophthalmologist will be masked to the study treatment and study eye randomization (see § 6.3)

The exact times of study drug administration, and comments, will be recorded on the appropriate page of the eCRF.

rhNGF 20 µg /mL:

For subjects randomized to rhNGF group:

Study Eye

- **Day 1:** One drop instilled into study eye (35 µL, corresponding to 0.70 µg of rhNGF).
- **Day 2, 3, 4, 5, 6:** One drop six times a day (every 2h) into study eye (210 µL, corresponding to 4.20 µg of rhNGF).

Total dose in the study eye will be 31 drops (1085 µL, equivalent to 21.7 µg rhNGF) over 6 days .

Vehicle:

For subjects randomized to vehicle group:

Study Eye

- **Day 1:** One drop instilled into study eye (35 µL, corresponding to 0 µg of rhNGF).
- **Day 2, 3, 4, 5, 6:** One drop six times a day (every 2h) into study eye (210 µL, corresponding to 0 µg of rhNGF).

Total dose of placebo vehicle in the study eye will be 31 drops (1085 µL, 0 µg rhNGF) over 6 days.

Fellow (non-study) Eye

For all subjects (subjects randomized to rhNGF group and subjects randomized to vehicle group):

- Day 1: One drop instilled into fellow eye (35 μ L, corresponding to 0 μ g of rhNGF).
- Day 2, 3, 4, 5, 6: One drop six times a day (every 2h) into fellow eye (210 μ L, corresponding to 0 μ g of rhNGF).

Total dose of placebo vehicle in the fellow eye will be 31 drops (1085 μ L, 0 μ g rhNGF) over 6 days.

5.5 Criteria For Schedule Adjustment/Dose-Modification/ Discontinuation Of Investigational Product

No schedule adjustment or dose adjustments are allowed.

5.6 Accountability Of The Investigational Product

The Pharmacist and/or Investigator will confirm the receipt of the IMP supply in writing by signing and dating standard drug accountability forms.

The Pharmacist and/or Investigator will keep a cumulative inventory and dispensing records, and will maintain all supplies under adequate security.

An accurate drug disposition record will be kept, specifying the date and amount dispensed to each subject.

Adequate record of receipt and use or loss of drug will be retained. This inventory record must be available for inspection by the Sponsor and regulatory inspection at any time. Copies of this record will be provided to the Sponsor by Cromsource throughout the duration of the study.

At the end of the study, unused IMP will be returned to Dompé for disposal.

5.7 Concomitant Medication

As a general rule, no medication other than study drug will be given during the course of the study, i.e., from the initial day of Screening until all of the final study evaluations have been completed.

Following the first dose of study drug, the exceptions are the medications allowed in § 4.2 Exclusion Criteria, under Exclusion Criterion 5:

- Vitamins and mineral supplements not containing other substances are allowed until 96 hours before each dose if considered by the Investigator unlikely to interfere with the study results.
- Paracetamol at doses of at most 2 grams per day and ibuprofen at doses of at most 1200 mg per day for no more than 3 consecutive days or 6 non-consecutive days are allowed.
- Oral, injectable and implantable hormonal contraceptives are allowed without restrictions for female subjects.

Decisions regarding subjects requiring concomitant medication will be discussed with the sponsor on a case-by-case basis. The administration of any such medication (including over-the-counter medications and vitamins) will be clearly documented on the Prior and Concomitant Medications eCRF page.

5.7.1 Prior and concomitant medications

Before the administration of the first dose of study drug, the following medications have the following exclusion periods specified in § 4.2 Exclusion Criteria, under Exclusion Criterion 5 and 12.

Within 96 hours before each dose:

Vitamins and mineral supplements not containing other substances are allowed if considered by the Investigator unlikely to interfere with the study results.

Within 14 days before the first dose of study drug:

Administration of any topical ocular (prescription or over the counter including artificial tears) or systemic medication including herbal product or fish oil preparations.

Within 30 days

Subject has corticosteroid sporadically, whichever the route of administration

Any medication by ocular or nasal administration route.

Exclusion periods apply for the following prior medications:

- a. amiodarone and hydroxychloroquine (210 days),
- b. monoclonal antibodies/ immunoglobulins/ other therapeutic proteins (120 days)
- c. Experimental drugs with a half life known to the Study Unit: Five half lives plus 2 weeks
- d. Experimental drugs with a half life unknown to the Study Unit: 120 days
- e. chloroquine and flunarizine (100 days)
- f. fluoxetine (75 days),
- g. benzodiazepines different from midazolam, lorazepam and triazolam, chlorpromazine, mephenytoin, nortriptyline, phenobarbital, primidone, carbamazepine, phenytoin and phenprocoumon (35 days).

6 ASSIGNMENT OF SUBJECT NUMBER

After obtaining informed consent a 3 digit consecutive screening number will be assigned to each subject according to the sequence of study entry, starting from from S001.

6.1 Randomisation

A total of 30 subjects will be randomized: 20 subjects on rhNGF treatment group and 10 on Vehicle treatment group.

Eligible subjects will be randomized at the Baseline Visit in a 2:1 ratio to a respective treatment group according to the randomization code and determined by the allocated randomization number. Randomization will be stratified by gender to ensure a balanced (2:1) gender distribution between treatment groups. With at least 6 subjects be recruited for each gender, it is ensured to have at least 4 male and 4 female subjects in the rhNGF group and 2 male and 2 female subjects in the Vehicle group.

Moreover, the study eye will be randomized for each subject to left and right eye.

During randomization, each subject will be allocated with randomization number. Together with the randomization number, the randomized study eye and associated kit number will be provided.

Randomization list and study eyes as well as associated kit numbers will be generated by a member of Cromsource SAS programming group not involved in the conduct of the study. A total of 60 kits (containing the treatment for right and left eye) will be supplied to the Pharmacy of the Clinical Unit.

Subjects will be assigned to treatment in numerical order. A tear-off label from the kit box, with the kit number, will be attached to the investigational product dispensing log.

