6.3 Masking

The identity of the treatments will remain unknown to the subject, Investigator, site staff and Sponsor's clinical research personnel until the study is unmasked for the final statistical analysis (after data base lock) except in case of specific events that will require unmasking of the subject.

The vials containing rhNGF (20 µg /ml) or vehicle will be identical in appearance, and the contents of the vials will be indistinguishable. All staff directly involved in the analysis of study results will remain masked to treatment assignments while the study is in progress.

In the event of a medical emergency where the knowledge of subject treatment is required to provide the subject with appropriate care, Investigators will have the possibility to unmask the treatment assignment for a specific subject. . The Investigators are encouraged to contact Cromsource staff before becoming unmasked if there is sufficient time.

If the Investigator becomes unmasked for any reason, this information will be recorded on source data and in the eCRF of the study, specifying the date and the reason.

The investigator and Dompé Pharmacovigilance contact will be provided with Code Breakers, containing the treatment allocation, to be opened only in case of a medical emergency. Therefore, a copy of the sealed

code envelopes will be filed at the clinic, in a secure, locked place. The integrity of these Code Breakers will be checked by the monitor at the end of the study.

Unmasking events will be recorded and reported in the final study report.

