7.2.17 Pharmacokinetic Endpoints

Two validated ELISA tests performed at Dompé farmaceutici s.p.a. will be used for PK measurements. The original validated method (ELISA I) will be the same applied to the NGF determination in serum samples taken from studies NGF0112 and NGF0212. A new additional validated ELISA method (ELISA II) will be performed with the intention of improving the sensitivity in the determination of NGF serum levels.

Pharmacokinetics blood samples were taken on Baseline Visit 0 hr, 0.5 hr, 2 hr, 4 hr, 8 hr, 9 hr, 10 hr, 11 hr, 12 hr, 14 hr and 16 hr, for assessment of single dose scheme at D1 Pre-Dose, 0.5 hr, 2 hr, 4 hr, 8 hr, 9 hr, 10 hr, 11 hr, 12 hr, 14 hr and 16 hr, for multiple dose scheme at D2 Pre-Dose, 0.5 hr, 2 hr, 4 hr, 6hr, 8 hr, 9 hr, 10 hr, 10.5hr, 11 hr, 12 hr, 13hr, 14 hr and 16 hr, D3 Pre-Dose, 2 hr, 4 hr, 6 hr, 8 hr, 10 hr, D4 Pre-Dose, D5 Pre-Dose, D6 Pre-Dose, 4 hr, 8 hr, 10 hr, 10.5hr, 11 hr, 12 hr, 13 hr, 14 hr and 16 hr, FU1 0hr, FU2 0 hr and 8 hr, FU3 0hr.

The assessment times are documented on eCRF Pages “Pharmacokinetics – Anti-Therapeutic Antibodies”, the rhNGF serum concentration assessed via both ELISA methods will be provided as external Excel files by Dompé. To maintain masking, these files will be provided for BDRM purposes in a masked manner by utilizing a dummy subject identification. For the final analysis, the Excel Files will contain the correct subject identification number.

The concentration versus time profiles of NGF will be assessed from individual serum samples of all subjects. As a general principle, the nominal assessment times will be used.

For the rhNGF serum levels according to ELISA I and ELISA II time-matched changes from baseline will be presented for the PKS (excluding blood samples at 6 hr, 10.5hr and 13 hr).

For this purposes, values below the limit of detection will be set to a value of 1 pg/ml. However, for listings values below the limit of detection will be presented as “< 32 pg/ml” for ELISA I levels and ‘< 15 pg/ml’ for ELISA II.

A binary variable ‘Presence of rhNGF’ will be derived for each ELISA with ‘No’ indicating a value below the limit of detection and ‘Yes’ indicating a value above the limit of detection.

Beyond the respective rhNGF plasma levels for both ELISA methods, the following parameters will only be investigated for each ELISA method, if the data warrant to do so:

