8.3.3 Data Review

In order to perform the statistical analysis of the final analysis, a decision needs to be made on evaluability of subjects and visits prior to locking the database and breaking the code for the masked study medication. In particular, a review of protocol deviations is required to evaluate the validity of planned analysis needs to be identified and corresponding actions needs to be defined, if any. This will be done at the Blind Data Review Meeting.

Performance of the Blind Data Review Meeting will require a clean database, i.e. all data are available including masked PK data of both assays, coded and no data queries are open.

No data entry should be performed between the data base Soft Lock and database lock. Exception would be Queries, which raised during the BDRM requiring a solution before data base Lock.

The scope of the BDRM will be:

- Evaluation of Re-Screened subjects
- Check correct assignment of allocated treatment and study eye
- Check protocol deviations and define analysis sets
- Review and confirmation of AESIs (sight threatening events)

More details on scope and performance of data review meetings will be described in a separate BDRM plan.

After the BDRM was performed, all decisions were summarized in BDRM Minutes, which were approved before the database was locked for the analysis.

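### Does the plan leave the study eye unmasked because it does not say who is told which eye it is?

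*Protocol*

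**What the plan says.** Protocol 5.4.2 (Dose regimen) sets the rule: "Both the subjects and the investigator/ophthalmologist will be masked to the study treatment and study eye randomization (see § 6.3"). It also fixes the other eye's treatment in every subject: "The fellow (non-study) eye will receive vehicle".

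Protocol 6.1 (Randomisation) describes what comes out of randomisation: "Together with the randomization number, the randomized study eye and associated kit number will be provided". No recipient is named. The list is produced by a CRO programmer who has no part in running the study.

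Protocol 6.3 (Masking) covers treatment identity: "The identity of the treatments will remain unknown to the subject, Investigator, site staff", and also the sponsor's clinical research personnel, until after database lock. It goes on to matching vials, emergency unmasking and code breakers. The study eye is not mentioned. Protocol 9.4 repeats the masking of treatment identity and extends it to CRO staff other than pharmacovigilance.

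SAP 8.3.3 (Data Review) lists, in the scope of the blind data review meeting, "Check correct assignment of allocated treatment and study eye". The decisions of that meeting fall "prior to locking the database and breaking the code for the masked study medication". Further detail "will be described in a separate BDRM plan". For the pharmacokinetic files at the same meeting, SAP 7.2.17 does state a route: "To maintain masking, these files will be provided for BDRM purposes in a masked manner by utilizing a dummy subject identification".

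**The concern.** The cross-reference from 5.4.2 leads to a section that does not deal with the study eye. Section 6.1 releases the eye in the passive voice, Protocol 5.4.1 has the investigator apply the drops, and Protocol 7.2 lists randomisation among the Day 1 procedures. A reader could infer that the person who doses, and who must be masked to the eye, is the one who receives it. The two role lists also differ: 5.4.2 names two groups for the study eye and 6.3 names four for treatment identity. The SAP adds a check of the study eye before code break and protects only the PK files explicitly.

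The stake is knowledge of treatment at eye level. A subject or examiner who knew the study eye would know that the other eye had vehicle. That could colour the between-eye VAS differences (a secondary tolerability endpoint, SAP Table 14.3-1.4), the ocular TEAEs by eye, and the investigator's causality rating of events in an eye known to be vehicle-only.

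**Working it through.** **What disclosure would reveal.** Inputs: 30 subjects, 20 on rhNGF and 10 on vehicle (Protocol 6.1); two eyes each; fellow eye always vehicle (5.4.2). Left and right are assumed equally likely to be the study eye.

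- Allocation: 30 × 2/3 = 20 and 30 × 1/3 = 10, which reproduces the protocol's split.
- Eyes: 30 × 2 = 60, of which 20 are active and 40 vehicle.
- Study eye unknown: P(a given eye is active) = 2/3 × 1/2 = 1/3. Treatment is certain for 0 of 60 eyes.
- Study eye known: P(study eye active) = 2/3 and P(fellow eye active) = 0. Treatment is certain for 30 of 60 eyes, which is 30 of the 40 vehicle eyes.
- P(subject on rhNGF) = 20/30 = 0.667 in both cases, so the arm is not revealed.

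**Data that would be exposed.** SAP 7.2.7 lists ten VAS times, one of them before the first dose, leaving nine. Nine times × 7 symptoms = 63 between-eye differences per subject, and 63 × 30 = 1,890 in all. The overall score is the mean of the same seven and adds no collected data. These are counts, not a size of bias; the documents give no basis for one.

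**Is disclosure already barred?** The argument takes three steps.

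1. The fellow eye is vehicle in everyone, so learning the study eye means learning the treatment of one eye.
2. Sections 6.3 and 9.4 withhold treatment identity from the subject, investigator, site staff, sponsor clinical personnel and (9.4) CRO staff other than pharmacovigilance.
3. Releasing the study eye to any of these people would therefore breach 6.3 or 9.4. Section 5.4.2 states the rule outright for subjects and assessors; the other two sections reach the remaining groups by consequence. This also explains why 5.4.2 refers to 6.3.

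**Can dosing be done without knowing the study eye?** Yes. Each subject box holds a separate box of six vials for each eye (Protocol 5.3). Vials and kit boxes carry the eye to be dosed, right or left (5.3.1). Rh-NGF and vehicle vials look alike and their contents cannot be told apart (6.3). Staff need only the label.

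**Does the SAP check need the eye to be shown?** Nothing says so. The check covers allocated treatment and study eye in one item. If listing it meant revealing the eye to the meeting, it would equally mean revealing the arm, which a blind meeting held before code break cannot do. SAP 7.2.2 and 7.2.4 obtain the study eye through the randomisation number, so the comparison can be run against the list by someone outside the masked team. PK files are a different case: a measured concentration can itself point to the arm, which is a good reason to spell out their handling.

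**The case for a change.** The strongest case for acting is that the gap is real and cheap to close. Section 6.3 does not mention the study eye, 6.1 names no recipient, and labels that make masked dosing possible do not by themselves withhold the eye. Protocol 8.12 also tells the visual-acuity examiner to occlude the fellow (non-study) eye. Eye-level contrasts are prespecified, the VAS is self-administered, and the investigator rates causality. That the analysis is descriptive does not make unmasked self-report harmless.

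The textual observations stand. The inference from them does not. Reading 6.1 as release to the masked persons would set it directly against 5.4.2, when the passive wording fits release to someone else equally well. In 8.12 testing starts with the right eye and the right eye is then covered before the left is tested, so the term there can only sensibly mean the eye not being tested. Any harm would need someone to break an explicit rule, and another sentence restating that rule would alter no analysis, table or estimate.

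Even then the design offers a check. Subjects who knew their study eye but not their arm would carry the same expectations in both groups, and the vehicle group, with vehicle in both eyes, would show them. SAP 10.6.2 already summarises the between-eye differences by treatment.

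**Conclusion.** No change to the plan follows. This is incomplete wording that the rest of the protocol fills: 5.4.2 masks the study eye for subjects and assessors, 6.3 and 9.4 bar its release to the other masked groups by consequence, and the packaging makes masked dosing workable. The method of the pre-lock check is properly left to the plan for the review meeting.

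If the rules were broken, treatment would be known for 30 of 60 eyes. The arm would stay masked at 0.667, and the primary study-eye comparison between arms would not be exposed to differential knowledge. The effect would fall mainly on secondary descriptive summaries; SAP 8.2 plans no inferential analysis. No loss of masking, bias or altered result is shown.

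This rests on two assumptions: that 5.4.2, 6.3 and 9.4 are followed as written, and that the Pharmacy Manual, the review meeting plan and the Protocol Clarifications, none of which was available, do not direct otherwise.

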6.2 Treatment Allocation

Each randomized subject will receive masked study treatment (either rhNGF eye drops 20 µg /ml or vehicle solution) in the study eye and vehicle in the fellow (non-study) eye according to the randomization code and determined by the allocated randomization number.

6.3 Masking

The identity of the treatments will remain unknown to the subject, Investigator, site staff and Sponsor's clinical research personnel until the study is unmasked for the final statistical analysis (after data base lock) except in case of specific events that will require unmasking of the subject.

The vials containing rhNGF (20 µg /ml) or vehicle will be identical in appearance, and the contents of the vials will be indistinguishable. All staff directly involved in the analysis of study results will remain masked to treatment assignments while the study is in progress.

In the event of a medical emergency where the knowledge of subject treatment is required to provide the subject with appropriate care, Investigators will have the possibility to unmask the treatment assignment for a specific subject. . The Investigators are encouraged to contact Cromsource staff before becoming unmasked if there is sufficient time.

If the Investigator becomes unmasked for any reason, this information will be recorded on source data and in the eCRF of the study, specifying the date and the reason.

The investigator and Dompé Pharmacovigilance contact will be provided with Code Breakers, containing the treatment allocation, to be opened only in case of a medical emergency. Therefore, a copy of the sealed

code envelopes will be filed at the clinic, in a secure, locked place. The integrity of these Code Breakers will be checked by the monitor at the end of the study.

Unmasking events will be recorded and reported in the final study report.

